### **Exploratory endpoints**

- Skin condition measured by Decision Tree Score (0-3) based on Peristomal Skin Health (OST 2.0)
- Quality of Life WHO5 score (0-100) based on Mental wellbeing (WHO5)
- Worry about leakage (5-point scale)
- Feeling of security (5-point scale)
- Technical assurance/interoperability measured by system reliability, notification frequency and stability (all measures on 5-point scales)
- Usability and self-management evaluated through System Usability Score (0-100) and confidence measures (5-poins scales)
- Preference, recommendation and future use (5-point scales)
- Adverse events

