### 3.2. Hypotheses

The study will explore if the Test Product leads to a significant decrease in incidents of leakage outside the baseplate compared to the period before entering the study and thereby possibly lead to secondary benefits such as improved feeling of leakage control, confidence, and security. Moreover, the Test Product may assist patients in managing their stoma and better understand general health aspects related to their condition, such as prevention of peristomal skin complications.

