### 4.5. Intended use of the device in the clinical investigation

### Intended purpose of device:

The Heylo™ is intended to be used together with an ostomy baseplate and bag, to detect and notify user of the occurrence of output leakage under an ostomy baseplate.

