### Evaluation of Heylo device (Questions, scale and assessment time Appendix 8, D)

- Technical assurance/ interoperability
  - Reliability and timing of notifications
  - System stability
- Usability/interoperability
  - Usability and ease of use evaluated through System Usability Score (0-100) (Appendix 7)
  - Other evaluations of self-management, and self-confidence
    - o Easiness in knowing when to change appliance
    - Confidence at night
    - o Peace of mind
    - o Adverse events

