| ن
3 | Worry about leakage  Think back on the last 2 weeks, to which degree did you worry about leakage? Very high degree - High degree - Some degree - Low degree - Very low degree In the last all | Subject                 | × |   | × |   | × |   |   |
|        |   |                         |   |   |   |   |   |   |   |
| C.3.1  | Worry about leakage  Only answered by subjects who have answered "Very high degree - High degree - Some degree" worry of leakage (C4).  | Subject                 | × |   | × |   | × |   |   |
|        | Why did you worry about leakage? (please tick all that apply (odour, embarrassment, soiling of clothes/bed sheets, skin issues, pain, other)  |                         |   |   |   |   |   | _ |   |
| C.4    | Feeling of security How is your feeling of security? Very poor, Poor, Acceptable, Good, Very good   |                         | × |   | × |   | × |   |   |
| පි     | Adverse Events (see termination form - ongoing)   | Nurse                   |   |   |   |   |   |   | × |
|        |   |                         |   |   |   |   |   |   |   |

| ۵   | D. Evalu   | Evaluation of Heylo device | e                      |                    |         |                    |             |                       |              |
|-----|--|----------------------------|------------------------|--------------------|---------|--------------------|-------------|-----------------------|--------------|
|     | Technical assurance/interoperability   |                            |                        |                    |         |                    |             |                       |              |
| 0.1 | Reliability of notifications  To which degree did you find the notifications from the App reliable and trustworthy? Not at all/Very low degree; Low degree; Some; High degree; Very high degree  |                            |                        |                    |         |                    |             | ×                     |              |
| D.2 | To which degree did you receive notifications timely to react on leakage? Not at all/Very low degree; Low degree; Some degree; High degree; Very high degree                                     |                            |                        |                    |         |                    |             | ×                     |              |

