| D.3 | How stable did you find the overall system in everyday use?
Very unstable; Unstable; Somewhat stable; Stable; Very stable   | Subject                    |                        |                    |         |                    |             | ×                     |              |
| Ö   | Registration/measurements  | PERFORMED BY               | Visit 1
(0
days) | Visit 2
4 weeks | 6 weeks | Visit 3
8 weeks | 10
weeks | Visit 4 Termina- tion | Ongo-
ing |
|     | Usability/Interoperability   |                            |                        |                    |         |                    |             |                       |              |
| D.4 | System Usability Score (SUS), Appendix 7   | Subject                    |                        |                    |         |                    |             | ×                     |              |
|     | Evaluation of self-management  | ю                          |                        |                    |         |                    |             |                       |              |
| D.5 | To which degree did the Test Product make it easier to know when to change baseplate compared to only using usual stoma baseplate?  Much lower degree; lower degree; same degree; Higher degree. | Subject                    |                        |                    |         |                    |             | ×                     |              |
| D.6 | How was your confidence at night with Test Product compared to only using usual stoma baseplate? Much lower, lower, same, higher, much higher  | Subject                    |                        |                    |         |                    |             | ×                     |              |
| D.7 | To which degree did the Test Product give you peace of mind? Very low degree; Low degree; Some degree; High degree; Very high degree   | Subject                    |                        |                    |         |                    |             | ×                     |              |

|          | E. Evalua  | Evaluation of Heylo + Service                   | ice                    |                    |         |                    |             |                  |              |
|----------|--|---|------------------------|--------------------|---------|--------------------|-------------|------------------|--------------|

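### As printed, item D.5 (knowing when to change the baseplate) has two answers below 'same' but only one above it, so it cannot grade improvement; check it against the EDC form

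*Combined protocol and SAP*

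**What the plan says.** Appendix 8 (24.8), part D, item D.5 asks: "To which degree did the Test Product make it easier to know when to change baseplate compared to only using usual stoma baseplate". The printed answers are "Much lower degree; lower degree; same degree; Higher degree". The subject answers once, at Visit 4.

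Item D.6, on confidence at night, uses the same comparator and offers "Much lower, lower, same, higher, much higher".

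On scale length, the exploratory endpoints in the synopsis read: "Usability and self-management evaluated through System Usability Score (0-100) and confidence measures (5-poins scales". Section 5.3, under the evaluation of the device, lists "Easiness in knowing when to change appliance" together with confidence at night and peace of mind as the further evaluations of self-management and self-confidence. It gives no number of points for any of them.

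Section 10.1 says that individual questions are listed and summarised descriptively, with N and percentage for discrete variables. Section 10.4 sets no formal success criteria.

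**The concern.** D.5 is comparative, and the plan hopes for an answer above 'same'. Section 3.2 states that "the Test Product may assist patients in managing their stoma", and Section 4.5 gives the device's purpose as "to detect and notify user of the occurrence of output leakage under an ostomy baseplate". A device that warns of leakage should make it easier to know when to change. On that side the printed list has one grade; on the side where little is expected it has two.

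If subjects saw this list, someone helped a little and someone helped a great deal would tick the same box. The report could then say how many found it easier, but not by how much. A table with D.5 and D.6 side by side would invite a comparison that the two answer lists do not support.

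**Working it through.** No sample-size, power or significance calculation applies. The check is a count of printed answers, followed by an illustration of what merging the top two grades does.

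**1. Count of printed answers, Appendix 8**

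| Item | Below 'same' | Same | Above 'same' | Total |
|---|---|---|---|---|
| D.5 | 2 | 1 | 1 | 4 |
| D.6 | 2 | 1 | 2 | 5 |

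D.1, D.2, D.3 and D.7 are not comparisons with 'same', but each prints five answers. D.4 is the System Usability Score. D.5 is therefore the only graded single item in part D with four. One more answer at the top would give 2 + 1 + 2 = 5, which matches D.6.

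**2. Declared scale length**

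The synopsis attaches five points to confidence measures, within an endpoint on usability and self-management. Section 5.3 places D.5's topic in the same group as confidence at night (D.6) and peace of mind (D.7), both of which print five answers. Read together, these imply five points for D.5. Neither place says so for D.5 by name.

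**3. Illustration of the merge**

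The documents give no distribution for D.5. Assume that 2, 5, 23, 40 and 30% of subjects would choose the five answers from lowest to highest, and that with four options the last 30% would move to 'Higher degree' and nobody else would change.

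- Five-point mean: 0.02×1 + 0.05×2 + 0.23×3 + 0.40×4 + 0.30×5 = 3.91.
- Four-point mean: 0.02×1 + 0.05×2 + 0.23×3 + 0.70×4 = 3.61.
- Mean as a share of its range: (3.91 − 1)/4 = 73% on five points; (3.61 − 1)/3 = 87% on four.
- Share in the top category: 30% on five points; 70% on four.
- Share above 'same': 40 + 30 = 70% on five points; 70% on four.
- Below / same / above: 7 / 23 / 70% on either list.

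The raw mean falls, while the range-scaled mean and the top-category share rise. The three-way split does not move. What is lost is the 40/30 division within improvement.

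**The case against.** The strongest objection is that the fifth answer may have been lost when the chart was read from the PDF. The same chart has a garbled C.1 row and mislabelled item numbers. G.3 prints no 'Low degree', although the parallel G.4 does. This stands: the text alone cannot settle what subjects are shown. Against it, the D.5 row otherwise reads cleanly, with a complete question, a closing full stop, the respondent and the Visit 4 mark. The gap is therefore worth a query.

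The second objection is that the synopsis is a loose guide to scale length. It also calls preference, recommendation and future use 5-point, yet E.1 is a two-way choice and E.3 is Yes/No. This stands too. Five points for D.5 is an inference, and the asymmetry against D.6 is the firmer ground.

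Three stronger readings are tempting but not supported:

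- *The missing answer understates the benefit.* Only the raw mean falls in the illustration; the top-category share and the range-scaled mean rise. The direction depends on the metric.
- *D.5 is the item closest to the device's function.* The stated function is to detect and notify. D.1 asks whether notifications were reliable, and D.2 asks "To which degree did you receive notifications timely to react on leakage". Both are at least as close, and both print five answers.
- *The truncation will corrupt a planned analysis.* Nothing in Section 10.1 averages D.5 with other items or requires D.5 and D.6 on one scale.

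**Conclusion.** The point holds as a minor one. On the printed text, D.5 has four unbalanced answers where its sister item has five balanced ones and where the plan implies five. If it is administered that way, it cannot separate slight from large improvement and cannot be compared with D.6 category by category. Worse, same and better all remain reportable.

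The consequence is confined to one exploratory item, asked once at Visit 4 and summarised descriptively. The primary endpoint, the secondary endpoints, the power and the 5% level are unaffected. The percentages in the illustration rest on an assumed distribution and show only how each summary moves; they do not predict the trial's result. The conclusion is conditional on the EDC form matching the printed chart.

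**What to change.** 1. Compare D.5 with the original page of Appendix 8 and with the subject questionnaire in the EDC system.
2. If the fifth answer is absent from the questionnaire, add 'Much higher degree', which makes D.5 parallel to D.6. If it is present, correct the chart.
3. If any answers were collected on four options, report D.5 for all subjects as below, at or above 'same degree'. That split is valid for both lists.
4. Check G.3 in the same pass, since its printed list has no 'Low degree' while that of G.4 does.

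The cost is one response option or one line of text. Section 12 names a change of assessment method as an example of a significant change to be notified to the ethics committee, so the sponsor should decide whether an added answer falls under it and record the change in the Change Log.

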### Secondary objectives

- To evaluate patient stoma self-management
- To evaluate health and leakage related quality of life.
- To Assess patients' evaluation of the Test Product, including preference, interoperability and ease of use.

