### 5. Design of the clinical investigation

### 5.1. General

The investigation is a multi-centered, open labelled, single arm case study with an expected duration of the study of 12 weeks ±2 weeks.

The investigation aims to include minimum 60 and maximum 90 subjects within a 6-month recruitment period. Minimum 30 subjects are planned to be enrolled within the 3 months after surgery.

All visits (V) will be planned to be remote visits using Microsoft Teams, Skype or Face time, if technically possible. If a remote visit is not possible, a face to face meeting will be scheduled, either at subjects' own home or at site.

Subjects are asked to fill in surveys at baseline and after 4, 6, 8, 10 and 12 weeks of test product use. At V2, V3 and V4 a call from the study nurse will be made to the subjects. In this call study nurse will conduct relevant evaluations together with subject e.g. number of GP contacts, nurse contacts and evaluation of skin (see flow chart section 7.2).

V0: Inclusion

V1: Baseline demographics & evaluation (questionnaire) & Introduction to Test Product, start test period

V2-V4: Test visits. V4 is also termination visit

Vx: Follow up visits if needed

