### 6.3. Subject withdrawal criteria

The subject is allowed to withdraw from the investigation at any time for whatever reason without any consequences for their future treatment outside the clinical investigation. The Investigator may withdraw a subject from the investigation at any time if they judge it to be the subject's interest.

The investigator must withdraw a subject from the investigation due to:

- Noncompliance with the CIP impacting the scientific integrity of the investigation.
- If subject's safety and wellbeing is compromised by further participation.
- Subjects lost to follow-up. At least three documented attempts will be made to verify subjects lost to follow-up.

Withdrawn subjects will not be replaced by new subjects.

A subject who is withdrawn from the investigation, for any reason, will be encouraged to contact the investigator if problems arise that the subject believes are related to the clinical investigation. Subjects who have not experienced any adverse events will not be followed up. For subjects who experience adverse events, see section 18.5.

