### Analysis of endpoints, individual questions, and assessments

All endpoints and individual questions from questionnaires as well as assessments will be listed and summarized by descriptive statistics. If relevant, the summaries can be done by the information about the current stoma product (1P/2P; Flat, convex, concave; Brand).

The summaries for the endpoints and individual questions will be made for each time point (baseline, Q1, Q2 etc), separately. For relevant endpoints, the summaries will also be done by time since surgery and/or time since discharge from hospital.

Summary statistics for continuous variables are presented with N, Mean, SD (standard deviation), Median, Min and Max, where N denotes the number of subjects contributing with non-missing data. For discrete variables, summary statistics are presented with N and percentage, where percentage is based on the total number of

subjects/observations with non-missing data. If relevant, the summary statistics can also include a 95% confidence interval for the mean or the calculated percentage.

For the primary endpoint, a paired comparison between data from Visit 4 (or last visit after at least 4 weeks of use of Heylo™) and baseline data (V1) will be performed. If data can be normally distributed the comparison will be performed by a paired t-test.

The secondary and exploratory endpoints can be analyzed similar to the primary endpoint but including time since surgery or time since discharge from hospital as a covariate, if relevant.

Other summaries and analyses can be made, if relevant.

As it is an exploratory study no adjustment for multiple testing will be applied if statistical analyses are performed.

All statistical analyses and summaries are made with SAS version 9.4 (SAS Institute Inc., Cary, NC)

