### 10.2. Sample size

The study aims to recruit 60-90 subjects with expected drop-out rate up to 25%. It is assumed that 60-90 included subjects will be adequate for investigating the benefits of Heylo™ delivered together with the online support service.

With 60-90 subjects and a drop-out rate of 25% it is assumed that at least 45 subjects will have information about leakage outside the baseplate at baseline and after at least 4 weeks of using the Test Product. As the distribution of the numbers of leakage outside the baseplate is unknown, the sample size calculation is based on a worst-case calculation where the primary endpoint is evaluated as leakage outside the baseplate with in the last 2 weeks (Yes/No) instead of using the exact number of times with leakage. If this proportion is reduced from 27% at baseline as observed in Nafees 2018 [7] to 3% by end of study, we will have a power of 85% to detect the difference as statistically significant, when using a 2-sided paired exact test in the binomial distribution, testing on a 5% level.

Due to the exploratory nature of the study, drop-out subjects will not be replaced.

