| E.1      | Preference Which product solution do you prefer? Stoma appliance alone without Test Product; Stoma appliance with Test Product (Heylo+Service)   | Subject   |                        |                    |         |                    |             | ×                |              |
| E.2      | Reason for preference What is your reason for preference? (Please tick all that apply) Body fit; Ability to bend and stretch; Feeling of security; Feeling of confidence; Less fear of leakage onto clothes; Discreet to wear, Discreetness in leakage control; Better sleep; Less embarrassment; Other + text | Subject   |                        |                    |         |                    |             | ×                |              |
| E.3      | Future use of product
If the Test Product was available today, would you start using it?
(Yes/No)  | Subject   |                        |                    |         |                    |             | ×                |              |
| E.4      | Recommendation of product to others  How likely would you be to recommend Heylo to other people with ostorny? Not at allivery unlikely: Unlikely; Neither/nor, Likely; Very likely   | Subject   |                        |                    |         |                    |             | ×                |              |
|          | F. Evaluation  | Evaluation of Coloplast Charter Support Service | Support                | Service            |         |                    |             |                  |              |
|   | Did you call Coloplast Charter Support Service during the study period? (Yes; No)  | Subject   |                        |                    |         |                    |             | ×                |              |
| No.      | Registration/measurements  | PERFORMED BY                                    | Visit 1
(0
days) | Visit 2
4 weeks | 6 weeks | Visit 3
8 weeks | 10
weeks | Visit 4 Termina- | Ongo-
ing |
| F.2      | Have you received any calls from Coloplast Charter Support Service during the study period? (Yes; No)  | Subject   |                        |                    |         |                    |             | ×                |              |

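### Preference, usability, future-use and recommendation items are scheduled only at Visit 4 and nothing requires them from subjects who leave early, so these results may describe completers only

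*Combined protocol and SAP*

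**What the plan says.** The secondary objectives in the synopsis and section 3.1 include this one: "To Assess patients' evaluation of the Test Product, including preference, interoperability and ease of use". The subject-reported items that serve it are mainly in Appendix 8. Part D covers reliability, timeliness, stability, usability (D.4, "System Usability Score (SUS), Appendix 7"), knowing when to change, confidence at night and peace of mind. Part E covers preference (E.1, "Which product solution do you prefer"), reason for preference, future use (E.3, "If the Test Product was available today, would you start using it") and recommendation.

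Each of D.1-D.7 and E.1-E.4 carries one mark, in the Visit 4 / termination column. Section 5.1 states that "V4 is also termination visit", and the flow chart (section 7.2) and Appendix 9 put that visit at week 12.

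Section 10.1 bases percentages on "subjects/observations with non-missing data" and counts N for continuous variables in the same way. The ITT set keeps every exposed subject with information on at least one endpoint. Section 10.2 allows an "expected drop-out rate up to 25" per cent, and drop-outs are not replaced. Section 6.3, on withdrawal, says "Subjects who have not experienced any adverse events will not be followed up".

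**The concern.** A subject who leaves before week 12 can be in the ITT set on the strength of one earlier endpoint and still contribute nothing to any D or E result. The plan describes no exit questionnaire. The termination form in Appendix 8 is completed by the investigator, and its contents are not given.

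This differs from ordinary missing data on the primary endpoint. Leakage is asked at baseline and at weeks 4, 6, 8, 10 and 12, so section 10.1 can fall back on the last visit after at least 4 weeks of use. The same section lets the other endpoints be analysed similarly, but that gives nothing for D and E, because no earlier answer exists to carry forward.

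If some people leave because the device is unreliable or cumbersome, the reported shares who prefer it, would use it or would recommend it omit them. The sponsor reserves the use of the data for reimbursement or regulatory purposes (section 21.1), where a preference percentage could be read as applying to everyone who tried the device.

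**Working it through.** **Plan's own figures.** The documents give no expected value for any D or E item, so there is none to reproduce. The relevant count in section 10.2 does reproduce: 60 x (1 - 0.25) = 45. At the upper recruitment limit, 90 x 0.75 = 67.5, taken here as 67 answering and 23 not.

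**Inputs.**
- Exposed subjects: 60 or 90 (section 10.2), assuming that all those enrolled are exposed and in the ITT set.
- Proportion leaving, d: 25%, the plan's ceiling, with 10% and 15% for comparison. Section 10.2 ties its 45 to leakage data after at least 4 weeks; I assume the same 25% applies to answers at Visit 4.
- Share answering favourably among responders, p: assumed. 80% is used for illustration, with roughly 60% and 90% alongside.

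**Formulas.** If no leaver would answer favourably, the share among all exposed is p(1 - d). If every leaver would, it is p(1 - d) + d. The responder figure can therefore overstate by at most pd and understate by at most (1 - p)d.

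**Results at the 25% ceiling.**

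| Exposed | Answering | Favourable among answering | All leavers unfavourable | All leavers favourable |
|---|---|---|---|---|
| 60 | 45 | 27 (60.0%) | 27/60 = 45.0% | 42/60 = 70.0% |
| 60 | 45 | 36 (80.0%) | 36/60 = 60.0% | 51/60 = 85.0% |
| 60 | 45 | 40 (88.9%) | 40/60 = 66.7% | 55/60 = 91.7% |
| 90 | 67 | 54 (80.6%) | 54/90 = 60.0% | 77/90 = 85.6% |

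For the 80% case, maximum overstatement is 0.80 x 0.25 = 20 points and maximum understatement is 0.20 x 0.25 = 5 points. The exact 95% intervals are 65.4-90.4% for 36/45 and 46.5-72.4% for 36/60. They describe sampling error only and do not cover the missing answers.

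**Lower drop-out, p = 80%.**
- d = 15%: 0.80 x 0.85 = 68% to 68 + 15 = 83%; overstatement at most 12 points.
- d = 10%: 0.80 x 0.90 = 72% to 72 + 10 = 82%; overstatement at most 8 points.

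**Usability score.** D.4 is a 0-100 score summarised as a mean over non-missing values. The same people are absent, but there is no natural value to assign them, so no bound is offered.

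**The case against.** Four stronger readings are tempting, and the documents do not support them.

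*That everyone who gives up the device is left out.* A subject who stops using it but stays to week 12 is still asked. Section 6.3 does not make stopping the device a mandatory reason for withdrawal; it lists noncompliance that affects scientific integrity. The gap concerns people who leave the study.

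*That section 6.3 rules out asking leavers.* Its sentence on follow-up stands next to a referral to section 18.5 on medical care. It reads as safety follow-up after withdrawal and does not bar a questionnaire at the point of leaving.

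*That leavers can never enter the percentages.* The Appendix 8 column carries no week and is also the termination column, so a site could give the items at an early exit. That is possible, but nothing requires it. The flow chart fixes Visit 4 at week 12, and section 10.1 distinguishes Visit 4 from an earlier last visit. Section 5.6 lists several survey weeks for endpoint data in general, but section 5.3 points to Appendix 8 for when D and E are assessed.

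*That the results are biased towards the product.* The direction is not shown. The illustrative range runs on both sides of 80%, 25% is a ceiling, and the 20-point figure needs every leaver to be unfavourable. Some will leave for other reasons: section 6.1.2 itself links drop-out to limited life expectancy or palliative care and to planned reoperation or reversal.

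Other points for the plan also stand. Dissatisfaction before week 12 is partly captured through ongoing device deficiencies, technical-support and call-advisor logs, and size changes. These items are exploratory endpoints in a study without success criteria, and N is shown with each summary. Asking preference once, after full exposure, is defensible for those who reach that point. None of this supplies the leavers' own evaluation.

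**Conclusion.** The point holds as a gap in the schedule and the reporting. As written, D.1-D.7 and E.1-E.4 need be collected only at week 12, are summarised on whoever answers, and have no earlier value to fall back on, so the results may describe completers only and may favour the product. Under the illustrative assumptions (60 exposed, 25% without an answer, 80% preference among the 45 who answer), the share among all exposed could be anywhere from 60% to 85%. At 10% drop-out the overstatement is at most about 8 points. These are bounds and say nothing about the likely value. The primary endpoint, sample size and power are not affected. The change is worth making because it is cheap and the answers cannot be recovered reliably afterwards.

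**What to change.** **Collection.** In Appendix 8 and section 6.3, state that D.1-D.7 and E.1-E.4 are sent by the existing electronic link at early termination as well as at Visit 4, with voluntary response, and that the reason for leaving is recorded.

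**Reporting.** In section 10.1:
- Give the number of exposed ITT subjects without an answer for each item.
- For E.1, E.3 and E.4, show the responder percentage beside a lower bound with all exposed ITT subjects as denominator and non-responders counted as not favourable. Label it a bound, not an estimate, since someone who left because of illness or reversal has not rejected the device. For E.4, fix in advance which categories count as favourable.
- Report the usability score, the ordinal D items and E.2 on responders, with the number missing.

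**Cost.** One extra trigger of a questionnaire that already exists and some added rows in the tables. Response from leavers will be incomplete, and the lower bound will look less favourable than the responder figure. No visit, eligibility rule, sample size or primary analysis changes.
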